7.4 Other Assessments

7.4.1 Drug Concentration Measurements

Samples for total IgG trough levels measurements will be taken at the Screening Visit, before any infusion given at the study site and at the (early) Termination Visit; these samples will be analyzed at the local laboratory.

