
The first study (Screening) visit of SCGAM-03 with the first Octanorm infusion will be the same visit as the visit in Week 65 (End-of-Study Visit) of the study SCGAM-01.
 
Eligible patients who have completed the SCGAM-01 study and were treated with any other commercially available SCIG before the start of the SCGAM-03 study (e.g. owing to a delay in local IRB approval for SCGAM-03) are permitted to enter the SCGAM-03 study.
 
The maximum allowed intermission of IgG treatment after completion of the SCGAM-01 study and before the start of treatment in the SCGAM-03 study is 5 weeks.
 
Patients for whom the Week 65 visit of the SCGAM-01 study is not identical to the First visit of the SCGAM-03 study will undergo a separate Screening visit with relevant screening procedures. Only after the patient's successful Screening and enrolment into SCGAM-03 study will the first infusion of Octanorm be permitted.
 
Screening visit assessments, to be performed before the First infusion, will include: physical examination (including weight); blood sampling for hematology, clinical chemistry, viral markers and trough total IgG, urine sample for urinalysis and urine pregnancy test (females of childbearing potential only), and completion of the same QoL questionnaire as used in the SCGAM-01 study. Note that these examinations will, for most patients, be performed within the framework of the main study SCGAM-01 (End-of-Study Visit in Week 65), in which case they need not be repeated at the same visit for SCGAM-03.
 
Patients will stay at the study site during the infusion, vital signs will be measured just before the start of each infusion given at the study site, then within 1 hour after the end of the infusion.
 
The patient's diary for the coming period of the home treatment will be issued to the patients. Ongoing adverse events and any relevant concomitant medications will be recorded.
 
At all subsequent study visits, the patients will undergo the following examinations at the site before the start of infusion: physical examination (including weight), blood sampling for hematology and trough total IgG, clinical chemistry, urine sample for urinalysis, with a urine pregnancy test if indicated. The patient's diary will be collected and reviewed. Other study assessments will be performed as indicated in the Flow Chart of Study Events.
 
One week after the last infusion, for both regular or premature termination, a termination visit will be performed at the site with the following assessments: physical examination (including vital signs and weight), blood sample for hematology, clinical chemistry, viral markers, and trough total IgG; urine sample for urinalysis and urine pregnancy test (females of childbearing potential only); completion of the QoL questionnaire; collection and review of the patient's diary.
 
AEs and any changes in concomitant medications will be recorded throughout the study period.
	

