
Safety Analysis Plan:
 
The safety analysis will comprise descriptive statistics, tabulations and listings of all TEAEs, safety laboratory results, vital signs and physical examination findings. All reported AEs will be coded according to MedDRA.
 
For this extension study, any AE is regarded as treatment-emergent if the patient migrated from the main to the extension study without being treated with another IgG product. If another product was used between the two studies, then an AE in the extension study is classified as treatment-emergent if onset or worsening is after start of the infusion of Octanorm at the screening visit. Only TEAEs are accounted for in the analysis.
 
For each TEAE, the time relative to the start of the infusion will be calculated and the TEAE will be classified as temporally associated if the onset is during the infusion or within 72 hours after the end of the infusion.
 
All reported events will be listed and tabulated in full detail, in particular the following key figures will be presented for each age group and for the study as a whole:
 
 • Total number of TEAEs reported. 	

Name of Sponsor/Company: OCTAPHARMA, Pharmazeutika Prod.Ges.m.b.H., [name]	
Name of Investigational Product: Octanorm	Protocol Identification Code: SCGAM-03
Name of Active Ingredient: Human Normal Immunoglobulin	Edition / Date of Protocol: October 04, 2018

• Number of temporally associated TEAEs.• Infusion rate at the onset of temporally associated TEAEs (frequencies and percentages).• Narratives will be prepared describing each death, other SAEs, and other significant AEs that are judged to be of special interest because of clinical importance. 
The QoL data will be presented descriptively by visit, along with the change from screening (defined as the first infusion).
	

FLOW CHART OF STUDY EVENTS

ASSESSMENTS	Screening – First visit (Week 65 of SCGAM-01)	Octanorm Treatment Visits					Termination (ET)
	---	---	Every 12 Wks ⁴ [every 24 wks]	---	Every 12 Wks ⁴ [every 24 wks]	---	---
WEEKS	1	12	24, 36, 48 [36]	60	72, 84, 94, 108, etc [84, 108, 132, etc]	Final Infusion Visit	One week after last infusion
Informed consent, In-/exclusion criteria ³	x						
Body weight ³	x	x	x	x	x	x	
Physical examination ³ , vital signs ¹	x	x	x	x	x	x	x
IgG trough levels ³	x	x	x	x	x	x	x

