Hematology ³ (CBC, WBC differential, hematocrit, hemoglobin)	x	x	[Wk 36, only]	x	[every 24 wks]		x
Clinical Chemistry ³ (sodium, potassium, glucose, ALT, AST, LDH, total bilirubin, blood urea nitrogen, creatinine)	x	x	[Wk 36, only]	x	[every 24 wks]	x	x
Urine analysis ³ : pH, glucose, ketones, leukocytes, hemoglobin	x	x	[Wk 36, only]	x	[every 24 wks]	x	x
Viral markers ³ : HAV, HBV, HCV, HIV	x			x			x
Urine pregnancy test ² ; ³	x	x	[Wk 36, only]	x	[every 24 wks]	x	x
Infusion of IMP (on site)	x	x	x	x	x	x	
Check for local injection-site reaction	x	x	x	x	x	x	x
Patient diary hand-out and check	x	x	x	x	x	x	x
Quality-of-life questionnaire	x			x			x
Concomitant medication	x	x	x	x	x	x	x
Adverse events	x	x	x	x	x	x	x

¹ Measurements of the vital signs will be carried out before and after the infusion of IMP.

² For females of child-bearing potential.

³ Procedures are to be conducted before the IMP administration (if applicable).

⁴ Procedures marked with an "x" will be performed at every on-site visit which occur every 12-weeks. Procedures marked within brackets (eg, [Week 36] or [every 24 wks]) will only be performed at the study week within the brackets, which corresponds to every other on-site study visit.

TABLE OF CONTENTS

STUDY OUTLINE.....	2
FLOW CHART OF STUDY EVENTS.....	8
PROTOCOL SIGNATURES.....	9
TABLE OF CONTENTS	10
TABLE OF TABLES.....	13
LIST OF ABBREVIATIONS	14
1 INTRODUCTION.....	16
1.1 BACKGROUND.....	16
1.2 RATIONALE FOR CONDUCTING THE STUDY	18
1.3 BENEFIT-RISK STATEMENT	19
2 STUDY OBJECTIVES.....	20
2.1 PRIMARY OBJECTIVE.....	20
2.2 SECONDARY OBJECTIVES	20
3 INVESTIGATIONAL PLAN.....	21
3.1 PRIMARY AND SECONDARY ENDPOINTS.....	21
3.1.1 Primary Endpoint	21
3.1.2 Secondary Endpoints	21
3.2 OVERALL STUDY DESIGN AND PLAN	21
3.3 DISCUSSION OF STUDY DESIGN AND CHOICE OF CONTROL GROUP(S)	23
3.3.1 Study Design	23
3.3.2 Dosing	23
3.3.3 Control Group(s)	23
3.3.4 Target Parameters	23
3.3.5 Statistical Considerations	24
4 STUDY POPULATION	25
4.1 POPULATION BASE	25
4.1.1 Inclusion Criteria	25
4.1.2 Exclusion Criteria	25
4.2 PRIOR AND CONCOMITANT THERAPY	25
4.2.1 Permitted Concomitant Therapy	25
4.2.2 Forbidden Concomitant Therapy	26
4.3 WITHDRAWAL AND REPLACEMENT OF PATIENTS.....	26
4.3.1 Premature Patient Withdrawal	26
4.3.2 Patient Replacement Policy	27

4.4	ASSIGNMENT OF PATIENTS TO TREATMENT GROUPS	27
4.5	RELEVANT PROTOCOL DEVIATIONS	27
4.6	SUBSEQUENT THERAPY	27

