6.1.3 Termination Visit

One week after the Final Infusion Visit (after patient withdrawal or study termination by one of the events described in Section 6.2.3), a Termination Visit will be performed including the following assessments:

- General physical examination (including vital signs).
- Drawing of blood samples for safety laboratory parameters including viral markers.
- Drawing of blood samples for total IgG trough level.
- Urine sampling including urine pregnancy test (in females of childbearing potential only).

- Completion of QoL questionnaire.
- Collection and review of the patient diary as at the earlier visits (Section 6.1.2) with recording of any AEs and changes in concomitant medications.
- Assessment of any local infusion-site reactions.

After the final examination, the clinical study is considered completed for the patient. No further study-related assessments may be performed, unless safety concerns (e.g. ongoing AEs) require follow-up.

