6.1.4 Interpretation of Time Windows in This Study

For this study the following time windows apply (see Table 3):

Table 3: Time Windows Used in this Study

Time point	Time stated	Tolerance
On site Visits beginning with Week 12	Weeks 12, 24, 36, 48, 60, and each subsequent 12 week visit.	± 2 weeks
Interval between Last Treatment Visit and (early) Termination Visit	1 week	± 5 days
Blood and urine sampling	before IMP administration	-1 day
Octanorm infusions at patient's home	every week (= every 7 days) or bi-weekly (= every 14 days) at double the weekly dose	±2 days ±2 days

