7.3.4 Laboratory Safety Tests

For children the trial-related blood loss (including any losses in the maneuver) should not exceed 3% of the total blood volume during a period of 4 weeks and should not exceed 1% at any single draw. The total volume of blood is estimated at 80 mL/kg body weight.

The following laboratory tests will be performed during the course of the study to investigate the efficacy and safety and tolerability of Octanorm (Table 5). At each visit, laboratory tests are to be performed before infusion of Octanorm at the study site.

Table 5: Laboratory Tests and Time Points

Test	Timing	Laboratory
Total serum IgG trough levels	At screening and at all subsequent treatment visits.	Local
Hematology (complete blood count, WBC differential, hematocrit, hemoglobin)	At screening, at Week 12, continue every 24 weeks until the Final Infusion Visit, and at the Termination Visit.	Local
Clinical chemistry (sodium, potassium, glucose, ALT, AST, LDH, total bilirubin, blood urea nitrogen or blood urea, creatinine)	At screening, at Week 12, continue every 24 weeks until the Final Infusion Visit, and at the Termination Visit.	Local
Urinalysis: pH, glucose, ketones, leukocytes, hemoglobin.	At screening, at Week 12, continue every 24 weeks until the Final Infusion Visit, and at the Termination Visit.	Local
Urine pregnancy test (women of childbearing potential)	At screening, at Week 12, continue every 24 weeks until the Final Infusion Visit, and at the Termination Visit.	Local
Virology: HAV, HBV, HCV, HIV	At screening, at Week 60, and at the Termination Visit.	Local

WBC, white blood cells; ALT, alanine aminotransferase; AST, aspartate aminotransferase; LDH, lactate dehydrogenase; HAV/HBV/HCV, hepatitis A/B/C virus; HIV, human immunodeficiency virus.

Local laboratory determinations will be done at the individual study sites according to local procedures.

The normal ranges of each determination at each laboratory involved will be provided in the Clinical Report.

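### The US Protocol calls the Termination Visit IgG sample a trough, but it is not a pre-dose sample under either regimen, and the SAP has no rule to keep it out of trough summaries

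*Protocol*

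**What the plan says.** **Timing.** The Protocol Study Outline states: "One week after the last infusion, for both regular or premature termination, a termination visit will be performed at the site". The Flow Chart heads its Termination column "One week after last infusion". Table 3 in Protocol 6.1.4, in the row "Interval between Last Treatment Visit and (early) Termination Visit", gives 1 week with a tolerance of ±5 days. None of these depends on regimen. Protocol 5.4 allows infusions every week or every second week, each ±2 days.

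**Label.** Protocol 6.1.3 lists among the Termination procedures "Drawing of blood samples for total IgG trough level". The Study Outline, the Flow Chart and 7.4.1 ("before any infusion given at the study site and at the (early) Termination Visit") agree. Protocol 7.5 describes the IgG trough as the level before the next dose.

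**Sampling rule.** The Table 3 row "Blood and urine sampling" places samples before IMP administration, with a tolerance of -1 day.

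**Table 5.** Protocol 7.3.4 gives the IgG timing as "At screening and at all subsequent treatment visits". It does not name the Termination Visit for IgG, although it does for every other test.

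**SAP.** Section 3.2.2 lists total IgG trough levels as a secondary variable. Section 10 contains no IgG analysis. Section 11.4 summarises laboratory values and their changes from baseline by time point. The groupings in section 8 are age and sex, not regimen. Table shells are deferred (section 14), and section 8.4 allows further derivations to be described in the CSR.

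**The concern.** A trough is defined by its place in the dosing interval: the sample is taken just before the next dose. The Termination sample has no next dose, and its window is wide compared with either interval. A table row labelled trough at Termination would therefore combine three kinds of value:

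- bi-weekly values that nominally sit at mid-interval;
- weekly values near day 7, which are troughs in substance;
- values from either regimen displaced by up to five days.

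At stake is the last IgG figure in the report, and the change from baseline to it, which readers will naturally take as the end-of-study trough. The SAP contains nothing that would classify, exclude or flag these samples.

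**Working it through.** **1. Position in the interval (documents only).** I take the last treatment visit in Table 3 as the last infusion, as the Study Outline and Flow Chart do.

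- Window: 7 - 5 = day 2 to 7 + 5 = day 12.
- Bi-weekly: nominal position 7/14 = 50% of the interval; range 2/14 = 14% to 12/14 = 86%. Every permitted day is before day 14.
- Weekly: day 7 is the nominal trough. Day 2 is before the cited Tmax of 2.6 days (Protocol 1.1). Day 12 is five days past the 7-day interval.

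The mislabelling follows from this step alone. The rest only gives a size.

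**2. The protocol's own kinetic figures.** Protocol 1.1 gives about 4.5 days from Tmax to the next weekly dose, and a drop of about 10 to 20% at a 30-day half-life.

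- 7 - 62.6/24 = 4.4 days, which agrees.
- 1 - 2^(-4.5/30) = 9.9%, the lower end of the stated range.

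**3. Illustrative model.** One compartment, first-order absorption, steady state, bi-weekly dose twice the weekly dose:

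C(t) = D × ka/(ka - ke) × [e^(-ke·t)/(1 - e^(-ke·τ)) - e^(-ka·t)/(1 - e^(-ka·τ))]

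Here D = 1 with τ = 7, or D = 2 with τ = 14, and ke = ln 2/half-life.

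- Half-life 30 to 35 days (Protocol 1.1).
- ka solved so that weekly steady-state Tmax is 2.6 to 3.2 days. The lower value is from Protocol 1.1. The upper value is an assumption, to allow for the 3 to 6 day peak in Protocol 1.2.
- Endogenous IgG 0 to 40% of the weekly trough (assumption), added as a constant.

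Worked cell: half-life 30 days (ke = 0.0231/d), Tmax 2.6 days (ka = 0.45/d), no endogenous IgG. Common factors cancel in each ratio.

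- Bi-weekly, day 7 over day 14: (0.8507/0.2764 - 0.0429/0.9982) / (0.7236/0.2764 - 0.0018/0.9982) = 3.035/2.616 = 1.160.
- Weekly, day 2 over day 7: 5.970/5.653 = 1.056.
- Weekly, day 12 over day 7: 5.072/5.653 = 0.897.

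Over the whole grid:

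| Termination sample | Compared with | Difference |
|---|---|---|
| Bi-weekly, day 7 | own day 14 | +3.6% to +16% |
| Bi-weekly, day 12 | own day 14 | +1% to +5% |
| Weekly, day 2 | own day 7 | +1% to +6% |
| Weekly, day 12 | own day 7 | -3% to -10% |

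**4. Which end is more plausible.** Protocol 1.1 cites a weekly peak-to-minimum difference of 5 to 10% of the mean. Without endogenous IgG the model gives 4.9 to 5.6% at Tmax 2.6 days and 1.5 to 1.7% at 3.2 days. That favours the upper end; the later peak in Protocol 1.2 favours the lower. The documents do not settle it.

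**5. Pooled row.** Let p be the bi-weekly share, with everyone sampled on day 7 and levels expressed relative to the weekly trough. The ratio of the pooled mean to the true trough mean is [p·b7 + (1 - p)] / [p·b14 + (1 - p)]. Here (b7, b14) runs from (1.0175, 0.9825) to (1.0742, 0.9258).

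- p = 10%: +0.35% to +1.5%
- p = 25%: +0.9% to +3.8%
- p = 50%: +1.8% to +7.7%

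The documents do not give p.

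**The case against.** Several counter-arguments carry weight.

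- **Termination gets its own row.** Tabulation by time point should keep it apart from scheduled visits. That is so, but both regimens are still combined within the row, under a trough label.
- **Pooling is inferred.** The shells are deferred and later derivations may appear in the CSR. So pooling is what the SAP yields as written, not something it announces. A rule fixed now is better than one devised after the data are seen.
- **Nothing depends on it.** Protocol 9.2 makes all results descriptive, IgG is secondary, and the sample follows the last infusion, so it cannot guide in-study dosing. Regular completers have a pre-infusion sample at the Final Infusion Visit. All of this stands and caps the severity.
- **The pre-infusion rule is imperfect.** Under Table 3 a bi-weekly pre-dose sample may fall on day 14 - 2 - 1 = 11, which the model without endogenous IgG puts 3.3 to 7.0% above day 14. A Termination sample on day 12 would be nearer the trough. True, but pre-dose sampling is what 7.5 describes, and showing days since last infusion lets a reader see such cases.

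Two stronger readings are tempting. A reader might infer that the Termination row would reverse the direction of change for bi-weekly patients, because Protocol 3.3.2 predicts a slightly lower bi-weekly trough while the model puts bi-weekly day 7 at 1.7 to 7.4% above the weekly trough. That needs a weekly-dosing baseline and an unchanged dose. Protocol 5.4 permits individual titration, some patients enter from another SCIG (3.2), and no regimen contrast is planned. A reader might also infer that only bi-weekly values are affected; the ±5 day window shows otherwise.

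**Conclusion.** The point holds as a minor one. In the US Protocol the Termination IgG sample does not meet the protocol's own description of a trough under either regimen, and the SAP would summarise it as one. This conclusion rests only on stated visit and dosing intervals.

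The percentages rest on assumed kinetics and an assumed endogenous share. The pooled shift also depends on the unstated bi-weekly share and may be invisible. If the SD of individual change were 15 to 20% (assumption), the standard error of a mean in 35 patients would be 15/√35 = 2.5% to 20/√35 = 3.4%, more than the whole shift at a 10% share.

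Scheduled samples drawn before an infusion, including the Final Infusion Visit, are not in question. No test and no primary safety variable is touched. The Table 5 omission is a separate inconsistency and is not evidence for the timing point. The SAP also covers Canada under a separate protocol (SAP section 1) that was not available, so nothing is concluded for sites there.

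**What to change.** In the SAP:

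1. Define an IgG trough as a sample drawn before an infusion within the Table 3 sampling rule, including the screening sample.
2. Use the last such sample, normally the Final Infusion Visit, as the last on-treatment trough.
3. Exclude all Termination IgG values, weekly and bi-weekly alike, from trough summaries. Report them separately with regimen and days since last infusion.

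In the Protocol, reconcile the trough label and the IgG time points across the Study Outline, the Flow Chart, 6.1.3, Table 5 in 7.3.4, 7.4.1 and 7.5. Check the Canadian protocol for the same point.

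The cost is SAP wording and one derived variable from dates already collected; no visit, sample or dose changes. There would be no Termination trough row. For an early withdrawal without a Final Infusion Visit, the last trough may be about 12 weeks old, or somewhat more with the ±2-week visit tolerance. Pre-dose samples at the early tolerance limit would still count as troughs.

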7.4.2 Quality of Life Assessment

QoL assessments will be made using the Child Health Questionnaire-Parent Form (CHQ-PF50) from parent or guardian of patients <14 years of age and the SF-36 Health Survey in patients ≥14 years of age. The QoL assessments will take place at the screening, at Week 60, and at the (early) Termination Visit.

7.5 Appropriateness of Measurements

Safety will be monitored by standard assessments.

The therapeutic efficacy, defined as the prevention of SBI, is a very important clinical aspect of any IgG replacement therapy and best characterizes benefit to the patient.

Determination of the pre-next-dose trough level of IgG is a standard method for determination of the correct dose for the individual patient.

The QoL questionnaires are standardized, validated instruments that have been widely used in clinical studies, including studies with PI patients.

8 DATA HANDLING AND RECORD KEEPING

To ensure that data in the CRFs are accurate and complete and in accordance with source records, source data verification will be performed in accordance with Octapharma standards. The extent of source data verification will be defined in detail in the monitoring manual.

8.1 Documentation of Data

8.1.1 Source Data and Records

Source data are defined as all of the information related to clinical findings, observations, or other activities in the study, written down in original records or certified copies of original records. The investigator will maintain adequate source records (e.g., case histories or subject/patient files for each subject/patient enrolled). Source records should be preserved for the maximum period of time required by local regulations.

For each subject/patient enrolled, the investigator will indicate in the source record(s) that the subject/patient participates in this study.

All data entered in the CRF must be supported by source data in the subject/patient records with the exceptions listed in [Section 8.1.2](#).

The investigator will permit study-related monitoring, audit(s), IEC/IRB review(s) and regulatory inspection(s), by providing direct access to source data/records.

The investigator may authorize site staff (e.g., sub-investigators, nurses) to enter study data into the CRF. This must be documented in the “Delegation of Authority Log”, signed by the investigator.

The following data must be verifiable from the source records: patient’s inclusion in Study SCGAM-03, patient number, sex, weight, date of birth, written informed consent, medical history, main inclusion and exclusion criteria, local laboratory test results, PID relevant concomitant therapies (medication and non-drug therapy), any AE occurring in the course of the study, details of infusions (batch number, number of vials used, date, dose, rate and site(s)), date and reason for premature withdrawal (if applicable). As part of the source records, laboratory data will be reviewed by the Investigator, assessed as to their clinical significance, signed and dated.

8.1.2 Electronic Case Report Forms (eCRF)

For each patient enrolled, an eCRF will be completed within the electronic data capture (EDC) system and approved by the Investigator or an authorized sub-investigator.

Study-site staff (e.g. research nurse) will be responsible for entering patient data into the validated EDC system. All site personnel will be trained on the EDC system and study specific eCRF before receiving access to the live database for data entry. The site is also provided with the approved eCRF Completion Guidelines which will assist in data entry and data issues/questions. The site will be notified once the database is active to begin data entry. Additional site training may be provided as refreshers throughout the study, if needed. All persons allowed to enter or change eCRF data must appear on the delegation of authority log.

The following data may be entered directly into the EDC system, without prior record of source data, turning the eCRF into source: dates of blood sampling, vital signs.

If any errors in the eCRFs are found during the data review process discrepancies will be generated programmatically within the EDC system, and 'manual' queries will be generated by either a monitor or Data Management. The programmed checks fire automatically once an eCRF page is saved within the system. The outputs of the programmed checks are referred to as 'discrepancies'. Discrepancies are generated by the input of illogical eCRF data with the purpose to clarify the context or insertion of illogical or missing data with the site or designee.

All discrepancies (programmed and manual) will be submitted to the site personnel or monitor for the site within the EDC system. Once the site responds to a discrepancy, Data Management or the monitor will review the new or changed data to ensure an appropriate response and close the discrepancy within the system.

